9.2 Replacing Patients

Patients enrolled in the 3+3 part who withdraw before receiving any protocol therapy will be replaced.

In the expansion cohort, patients who come off study before the end of cycle 4 for any reason not related to toxicity (and prior to the first formal response assessment following cycle 4) will be replaced.

PROTOCOL TITLE: I 49217 - Phase 1 CDX-1401/ Poly-ICLC +Decitabine +Nivolumab in Patients with MDS or Low Blast Count AML

Patients who do not complete the study through Day 29 for reasons other than DLTs will be replaced.

10 TREATMENT

Treatments will be administered predominantly on an outpatient basis. Reported adverse events (AEs) and potential risks are described in Section 13. Appropriate dose modifications are described in Section 10.3.2. No other investigational or commercial drugs or therapies other than those described below may be administered with the intent to treat the subject for their myeloid neoplasms. Patients may receive all their usual medications.

[figure not shown]
10.1 Dosing and Administration

The vaccine is comprised of CDX-1401 (1 mg) given intracutaneously with 1.8 mg of Poly-ICLC. The first dose of the vaccine is given on Day -14 and then, on Day 15 of each decitabine cycle for the first 4 cycles (total of 5 vaccines). Thereafter, patients will receive a booster vaccine on Day 1 of every 4th cycle, indefinitely.

Nivolumab is to be given at a fixed dose of 3 mg/kg every 2 weeks starting on Day 1 of Cycle 1 through cycle 4 day 15. After cycle 5 nivolumab will be given as a flat dose of 480mg every 4 weeks on day 1 of each decitabine cycle (+/-7 day window). Nivolumab administration may continue on protocol until disease progression or the patient elects to discontinue nivolumab.

Decitabine/nivolumab cycles will be given on schedule every 4 weeks unless a delay is deemed clinically necessary by the treating physician/investigator. If the patient requires a delay of more than 6 weeks, they will come off study. The study schema is depicted in **Figure 3**.

Figure 3: Study Schema

For the purposes of this study, 1 cycle = 28 days and is comprised of 5 doses of IV decitabine (days 1-5), 2 doses of nivolumab during cycles 1-4 and 1 dose of nivolumab cycles 5 and above (day 1 and day 15 during cycles 1-4 or day 1 cycles 5 and above) and 1 vaccination (day 15). Protocol therapy may be given at the discretion of the treating physician within a +/-7 day window to accommodate patient’s preference, clinical judgement and schedule or outside this window after discussion with the PI.

Note: When nivolumab and decitabine are administered on the same day, decitabine is administered first, followed by nivolumab.

10.1.1 Vaccine (Anti DEC-205-NY-ESO-1 Fusion Protein (CDX-1401)/ Poly ICLC)

CDX-1401 and poly-ICLC will be administered on Day -14 prior to the first course of decitabine and *then Day 15 of every cycle for the first 4 cycles. After Cycle 4*, CDX-1401 and poly-ICLC will

PROTOCOL TITLE: I 49217 - Phase 1 CDX-1401/ Poly-ICLC +Decitabine +Nivolumab in Patients with MDS or Low Blast Count AML

be administered on Day 1 of every 4th cycle as a booster (i.e. on day 1 of cycles 8, 12, 16, 20, 24) (see study calendar below: Section 10.1.3).

The CDX-1401 will be given as an intracutaneous injection (a mixture of subcutaneous and intradermal administration, at a dose of 1 mg); poly-ICLC will be given subcutaneously at a flat dose of 1.8 mg on each day of CDX-1401 vaccination.

Administration: Within a vaccine treatment session (consisting of one intracutaneous administration of CDX-1401 with poly-ICLC) dosing should be given within the same administration site (a 5 x 5 cm area on the extremities or the abdomen). The administration site should be free of potentially complicating dermatologic conditions, and should not be located in an area where integrity of the draining lymph node bed is potentially compromised (i.e., an extremity where a nodal resection was previously performed). For each subsequent administration session, a new administration site should be selected, with the aim of stimulating a new draining lymph node bed for each of the five administrations (Note: After the first 5 vaccinations, the vaccine may be administered in location of patient's preference). All nurses administering this vaccine will be trained to administer the doses intracutaneously prior to study implementation.

Intracutaneous injections are a combination of intradermal and subcutaneous injection. The maximum volume which can be administered intradermally is 0.1 ml and the maximum volume administered subcutaneously is considered to be 1-2 ml. Intracutaneous injections are a combination of the standard subcutaneous (many drugs) and intradermal (like a TB test) routes which are in routine use throughout the hospital. Drug will be administered using a 25G or smaller needle of ¼ to ⅝ inches in length.

- *CDX-1401* will be administered via intracutaneous injection (with approximately half of the planned dose administered by each route). Each CDX-1401 dose will be administered in a maximum volume of 1 ml, and may be split into up to 4 intracutaneous injections given within the 5 x 5 cm administration site. An appropriate needle for intracutaneous administration (25-gauge or smaller) is recommended. We have suggested that the CDX-1401 be administered in 2 injections so that no more than 0.75 ml will be given in any one spot and to avoid excess administration of drug intradermal.
- Poly-ICLC dosing will consist of one subcutaneous injection of 1.8 mg, within the 5 x 5 cm administration site. Poly-ICLC will be administered as soon as possible after the CDX-1401 injections, with the goal to administer all drugs within a one hour period.

Note: Poly-ICLC drug product used to be labeled as 2 mg/mL but as per IB V.14 dated January 25, 2018, the labeled claim is being changed to incorporate a correction for the water content in the lyophilized components (Poly I and Poly C) and will now be listed as 1.8 mg/ml Poly-ICLC. This represents no change in the product or formulation, but simply a calculation correction. In effect, the prior 2.0 mg/mL label represented the “wet” Poly-IC concentration which is equivalent to the current 1.8 mg/mL label representing the “dry” Poly-IC concentration.

PROTOCOL TITLE: I 49217 - Phase 1 CDX-1401/ Poly-ICLC +Decitabine +Nivolumab in Patients with MDS or Low Blast Count AML

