The DEC-205 receptor has been shown to be an efficient mAb-based target to enhance the induction of strong Ag-specific immune responses and cross-presentation in mice (29) and humans (30). The receptor is also expressed on human monocyte-derived dendritic cells (DCs) along with other endocytic receptors, such as the mannose receptor/CD206 and DC-SIGN/CD209 [reviewed in (30)]. In a recent study at Roswell Park Cancer Institute, full-length NY-ESO-1 was fused to the C terminus of human anti-DEC-205 (DEC205mAb-NY-ESO-1 fusion protein) (10). Whereas non-targeted and antibody-targeted NY-ESO-1 proteins similarly activated CD4+ T-cells, cross-presentation to CD8+ T-cells was only efficiently induced by targeted NY-ESO-1 (10). In addition, DEC-205 targeting elicited specific CD4+ and CD8+ T-cells from peripheral blood lymphocytes of cancer patients. In this study, the DEC-205 mAb-NY-ESO-1 fusion protein will be directly injected subcutaneously in an effort to prime endogenous DCs with full length NY-ESO-1 full length protein and thereby sensitize the immune system to NY-ESO-1 induced in MDS cells following exposure to decitabine and nivolumab. Our previously completed phase I study has demonstrated that the combination of NY-ESO-1 vaccination with decitabine is safe.

A detailed discussion of the preclinical pharmacology, pharmacokinetics, and toxicology of Anti DEC-205-NYESO-1 Fusion Protein can be found in the Celldex Investigator's Brochure.

Poly-ICLC

Poly-ICLC (Hiltonol, manufactured by Dalton for Oncovir, Inc., to be provided by Celldex Therapeutics) is an experimental viral mimic and broad activator of innate immunity. While initially developed as an interferon inducer, poly-ICLC has much broader biological effects in humans, including specific antiviral, immune activating, vaccine adjuvant, and antitumor actions.

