32 DRUGS OR DEVICES

32.1 Vaccine (Anti DEC-205-NY-ESO-1 Fusion Protein (CDX-1401)/ Poly ICLC)

32.1.1 Active Substance and Source

CDX-1401

The clinical trial product will be formulated as a sterile solution intended for parenteral use. CDX-1401 will be provided in 2 ml vials containing approximately 1 ml of solution, at a concentration of 1 mg/ml.

Poly-ICLC

Poly-ICLC is an Investigational Product manufactured by Dalton for Oncovir, Inc. and supplied by Oncovir, Inc.

Poly-ICLC (polyinosinic-polycytidylic acid stabilized with poly-L-lysine and carboxymethylcellulose) is a synthetic double-stranded ribonucleic acid (dsRNA) with broad immune-enhancing effects mediated through TLR-3 activation.

Poly-ICLC will be provided in single-dose vials containing 1 ml of 1.8 mg/ml opalescent solution.

The poly-ICLC vials should be refrigerated at about 40°F (2-8°C) but should not be frozen. Poly-ICLC is also stable at room temperature for brief periods (days).

PROTOCOL TITLE: I 49217 - Phase 1 CDX-1401/ Poly-ICLC +Decitabine +Nivolumab in Patients with MDS or Low Blast Count AML

Because the product is not formulated with a preservative, once the sterile vials are entered or the poly-ICLC is drawn into a syringe, the drug should be used as soon as possible (typically within 6 hours if kept at room temperature or within 24 hours if refrigerated and the syringe(s) had been filled under aseptic conditions) or in accordance with any applicable institutional guidance. Poly-ICLC is to be withdrawn from the vial under sterile conditions and administered subcutaneously as supplied.

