32.1.3 Preparation

CDX-1401 will be provided as a 1 mg/mL solution. It will be given intracutaneously as outlined in Section 10.

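### Section 10.1.1: the suggested two-injection method for CDX-1401 cannot give the stated route split within the stated intradermal limit

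*Combined protocol and SAP*

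**What the plan says.** Section 10.1.1 describes CDX-1401 as an intracutaneous injection: "a mixture of subcutaneous and intradermal administration, at a dose of 1 mg". It sets the route split as "with approximately half of the planned dose administered by each route".

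The same section gives four figures that bear on whether that split can be reached:

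- An intradermal limit: "The maximum volume which can be administered intradermally is 0.1 ml". The corresponding subcutaneous figure is 1-2 ml.
- A total volume of at most 1 ml per dose.
- A permitted number of injections: the dose "may be split into up to 4 intracutaneous injections".
- A suggested number of injections and a per-spot volume: "CDX-1401 be administered in 2 injections so that no more than 0.75 ml will be given in any one spot". The other reason given for this suggestion is to avoid too much drug going intradermally.

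On supply, Section 32.1.1 states "CDX-1401 will be provided in 2 ml vials containing approximately 1 ml of solution, at a concentration of 1 mg/ml" and Section 32.1.3 repeats that "CDX-1401 will be provided as a 1 mg/mL solution". No dilution or concentration step is described. Section 10.4.1 allows no change to the vaccine dose.

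The background in Section 2.3.1 says only that the fusion protein "will be directly injected subcutaneously". Section 10.1.1 requires nurses to be trained in intracutaneous administration before the study starts, but does not say what they are taught about the split.

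**The concern.** Section 10.1.1 is the only place where the protocol tells staff how to inject the vaccine, and Section 32.1.3 refers back to Section 10 for it. Its figures do not fit together. The split asks for a large intradermal share, the limit points to a small one, and the suggestion of 2 injections is itself meant to hold the intradermal amount down. Nothing says which figure takes priority, or whether the 0.1 ml limit applies to each injection or to the whole session.

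What is at stake is whether delivery is uniform. The NY-ESO-1 antibody and T-cell responses are the secondary endpoint (Section 8.2) and are tested before and after treatment in 18 patients (Section 19.4). Each patient is scheduled for 5 priming vaccinations and then boosters every fourth cycle (Section 10.1), and up to two sites may take part (Section 6). If staff settle the conflict in different ways, patients may receive different mixtures of routes under one regimen name. Section 15 says that the immune results will be used to justify a larger study, which would need a vaccination procedure that can be repeated.

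**Working it through.** **Inputs**

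- Dose: 1 mg (Section 10.1.1; Table 5).
- Concentration: 1 mg/ml (Sections 32.1.1 and 32.1.3).
- Split: about half by each route (Section 10.1.1).
- Intradermal limit: 0.1 ml, basis not stated (Section 10.1.1).
- Injections: 2 suggested, at most 4 (Section 10.1.1).
- Per-spot volume: no more than 0.75 ml (Section 10.1.1).

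**Step 1: the volume that the split implies.** Dose volume = 1 mg ÷ 1 mg/ml = 1 ml, which agrees with the stated 1 ml maximum. Half of this is 0.5 ml intradermally. At 0.1 ml per deposit, 0.5 ÷ 0.1 = 5 deposits, against a maximum of 4.

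**Step 2: the most that the limit allows, read per injection.** For k injections, intradermal maximum = 0.1 × k ml, share = 0.1 × k ÷ 1, and the remainder goes subcutaneously.

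| Injections (k) | Volume per spot if even (ml) | Intradermal maximum (ml) | Share | Subcutaneous remainder (ml) |
|---|---|---|---|---|
| 1 | 1.00 (above 0.75) | 0.1 | 10% | 0.9 |
| 2 (suggested) | 0.50 | 0.2 | 20% | 0.8 |
| 3 | 0.33 | 0.3 | 30% | 0.7 |
| 4 (maximum) | 0.25 | 0.4 | 40% | 0.6 |

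**Step 3: the limit read as a session total.** The intradermal maximum is 0.1 ml whatever the number of injections, a share of 0.1 ÷ 1 = 10%, with 0.9 ml subcutaneous.

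**Step 4: the suggested method against the split.** Two even injections are 0.5 ml each. Giving half of each intradermally would be 0.25 ml per injection, and 0.25 ÷ 0.1 = 2.5 times the limit. Staying within the limit gives 20%, which is 30 percentage points short of half. With 4 injections the shortfall is 10 points.

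The subcutaneous remainder (0.6 to 0.9 ml) is within the stated 1-2 ml throughout, so the conflict is only on the intradermal side.

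**The case against.** The best defence is the word approximately. If the 0.1 ml limit applies to each injection, and 4 injections are used with each intradermal deposit at the limit, the share is 40%. That can be read as approximately half, and then the split, the limit and the count are all respected. The per-injection reading is also the more natural one, because the figure sits in a general description of technique next to a comparison with a TB test. This stands. A reader might infer that the instruction cannot be carried out at all, but the documents do not support that. The defence does not rescue the suggested 2 injections, since 20% is not approximately half.

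A reader might also infer a five-fold spread in the intradermal share, from 10% to 50%. This is too wide. The 50% end is outside the limit or the count. The 10% end needs either the session-total reading or a single 1 ml injection, which exceeds the per-spot volume. With a per-injection limit and 2 to 4 injections, the maximum share runs from 20% to 40%, a two-fold range.

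Four further points for the plan are fair:

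- Section 2.3.1 is background. The operative sections say intracutaneous, and Section 10.7 explains that as both routes combined. The wording is worth aligning but is not a competing instruction.
- Nurses are trained and there are at most two sites, so variation is a possibility and not an established fact. Because the content of the training is not given, the possibility remains open.
- The case report form is not among the documents. Section 18.1 says only that a study-specific database will be designed, so it cannot be said that route and volume go unrecorded.
- Nothing in the documents shows that the intradermal share changes the immune response. Section 2.3.1 reports no clear dose response in the earlier solid-tumour cohorts treated with 0.1 to 3 mg. That concerns dose and not route, but it gives no support for strong sensitivity to delivery.

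**Conclusion.** The point holds as an internal inconsistency in Section 10.1.1. With the suggested 2 injections and a per-injection limit, at most 20% of the dose can go intradermally, against a stated split of about 50%. With the permitted maximum of 4 the figure is 40%, which is arguable. With a session-total limit it is 10%. No other section resolves the conflict, so the intradermal share may differ between sessions, nurses or sites.

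This rests on one assumption: that the 1 mg dose is drawn from the 1 mg/ml vial without dilution or concentration, as Section 32.1 indicates. The percentages are maxima within the stated limit and not estimates of what patients will receive.

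A reader might go further and infer that the trial's conclusions are compromised. The documents do not support that. The primary endpoint is the DLT rate (Section 19.1), the total dose stays at 1 mg whatever the split, and no sample size or decision rule depends on the route. The immune analyses are secondary, summarised descriptively and tested within patients, and Section 19.3 already rules out comparison with historical controls. The inconsistency should be fixed, but it is not critical to the trial's primary purpose.

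**What to change.** The investigators and the vaccine supplier should reconcile four items in Section 10.1.1 into one instruction that can be carried out at 1 mg/ml and is used at every site:

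- the route split;
- the intradermal limit, stating whether it applies per injection or per session;
- the number of injections;
- the volume per spot.

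The background sentence in Section 2.3.1 should be brought into line with the result. This review takes no view on which split, limit or count is right.

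If the case report form does not already capture it, record for each vaccination the number of injections and the volume given by each route. The delivered regimen can then be described when the immune results are reported. An analysis of immune response by intradermal volume is not needed, since with at most 18 patients it would add little.

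The cost is a wording amendment, an update to training that the section already requires and, if needed, two or three data fields. No extra patients or procedures are involved.

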10.1.2 Nivolumab

Nivolumab will be given every two weeks (± 7 days) (four weeks (two doses of nivolumab) is equivalent to one cycle of nivolumab) at a dose of 3 mg/kg/dose for the first 4 cycles of decitabine, for cycles 5 and above, nivolumab, if continued, will be given at a flat dose of 480mg every 4 weeks on day 1 of each decitabine cycle. The dosing calculations should be based on the actual body weight. If the patient's weight on the day of dosing differs by $>10\%$ from the weight used to calculate the original dose, the dose must be recalculated. All doses should be rounded to the nearest milligram if dose rounding is allowed as per institutional guidelines. There will be no dose modifications allowed.

Administration: Nivolumab is to be administered as a 30-minute (+/- 10 minutes) IV infusion, using a volumetric pump with a 0.2-1.2 micron in-line filter at the protocol-specified dose. It is not to be administered as an IV push or bolus injection. Nivolumab injection can be infused undiluted (10 mg/mL) or diluted with 0.9% Sodium Chloride Injection, USP or 5% Dextrose Injection, USP to protein concentrations as low as 0.35 mg/mL. At the end of the infusion, flush the line with a sufficient quantity of normal saline.

Reported adverse events (AEs) and potential risks are described in **Section 13**. Appropriate dose modifications are described in **Section 10.4**.

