8 STUDY ENDPOINTS

8.1 Primary Endpoint

- To determine the safety of NY-ESO-1 vaccination (Anti-DEC-205-NY-ESO-1 fusion protein (CDX-1401)/poly ICLC) given in combination with decitabine and nivolumab.
 - This is a modified 3+3 design with a 12 patient expansion cohort at the maximum tolerated dose (MTD) or the maximum administered dose (MAD). We expect 18 patients to be enrolled (all at Dose Level +1(DL1)), given experience with these treatments in other studies. In DL1, decitabine will be given at 20 mg/m²/day,

PROTOCOL TITLE: I 49217 - Phase 1 CDX-1401/ Poly-ICLC +Decitabine +Nivolumab in
Patients with MDS or Low Blast Count AML

intravenously, over 1 hour on days 1-5 followed by 23 days without decitabine. If required, dose de-escalation of decitabine to 15 mg/m² is provided for during the safety portion of the study.

- The DLT window will begin on day -14 of cycle 1 and end on day 1 of cycle 2. The first cohort will enroll 3 patients and the DLT window for these 3 patients will end when the last patient in this group has reached cycle 2 day 1 of therapy. A second group of 3 patients will then be enrolled and treated.

All AEs and DLTs will be collected and used for descriptive characteristics for the purposes of the study.

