10.1.3 Decitabine

Decitabine will be given starting at dose level 1, which is the standard dose and schedule currently in use: 20 mg/m²/day for 5 consecutive days following standard of care guidelines (50).

Decitabine will be given at 20 mg/m²/day, intravenously, over 1 hour on days 1-5 followed by 23 days without decitabine at the discretion of the treating physician per their standard practice. Delays in dosing are allowed per standard institutional practice. Decitabine should be given Days 1-5 unless a delay is deemed necessary by the treating physician for patient safety. If required, dose de-escalation of decitabine to 15 mg/m² is provided for during the safety portion of the study.

Table 5 Dose Levels

Dose Level	CDX-1401/Poly-ICLC	Decitabine	Nivolumab
1	1mg/1.8mg	20mg/m ² days 1-5	3mg/kg days 1,15
-1	1mg/1.8mg	15mg/m ² days 1-5	3mg/kg days 1,15

There will be no dose modifications to the decitabine dose during the first 8 cycles of treatment. After cycle 8, dose reductions may be made at the discretion of the treating physician per their standard practice, but cycles should be given every 4 weeks unless a delay is deemed necessary by the treating physician for patient safety.

Delays in dosing up to 6 weeks are acceptable if deemed necessary for patient safety. Grade 4 neutropenia, transfusion dependence for platelets and red blood cells and the possibility of hospitalization for infections are expected toxicities of the underlying disease process and of standard treatment with decitabine.

Please see below for a detailed study calendar:

PROTOCOL TITLE: I 49217 - Phase 1 CDX-1401/ Poly-ICLC +Decitabine +Nivolumab in Patients with MDS or Low Blast Count AML

Treatment Plan: Cycle 1

Cycle 1														
Day	-14	1	2	3	4	5	6	7	8	...	15	...	28
CDX-1410	X											X		
Poly ICLC	X											X		
Decitabine (DAC)			X	X	X	X	X							
Nivolumab (NIVO)			X									X		

Treatment Plan: Cycles 2-4

Cycles 2-4														
Day	1	2	3	4	5	6	7	8	9	10	...	15	...	28
CDX-1410												X		
Poly ICLC												X		
Decitabine (DAC)	X	X	X	X	X									
Nivolumab (NIVO)	X											X		

PROTOCOL TITLE: I 49217 - Phase 1 CDX-1401/ Poly-ICLC +Decitabine +Nivolumab in Patients with MDS or Low Blast Count AML

Treatment Plan: Non-Vaccine Cycles:

Cycles 5-7, 9-11, 13-15, 17-19, 21-23, 25...														
Day	1	2	3	4	5	6	7	8	9	10	...	15	...	28
CDX-1410														
Poly ICLC														
Decitabine (DAC)	X	X	X	X	X									
Nivolumab (NIVO)	X													

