10.3 Definition of Dose-Limiting Toxicity

Dose limiting toxicities (DLTs) are defined as any non-hematologic grade 4/5 toxicities that are definitely, probably, or possibly related to the administration of the investigational agent(s) (see Appendix H for organ specific auto-immune grading of toxicity).

All AEs will be graded according to the NCI-CTCAE scale Version 4.0.

Hematological toxicities are expected in patients with MDS undergoing therapy with decitabine and will not be considered dose limiting. Hematological toxicities will not be deemed dose limiting, in agreement with other studies in patients with MDS and AML.

The initial DLT period will be defined as 28 days after the first dose of decitabine. Given that toxicities related to checkpoint inhibitors may not be immediately manifested, after the first 3 patients have been enrolled, accrual to the expansion cohort will be delayed to monitor for late developing toxicities until all patients in the first 3 patient cohort have been followed until cycle 4 day 29 of decitabine.

Patients will be monitored throughout the study and according to the schedule of procedures and observations. Any auto-immune related events which occur between days 29 and the end of study may be sufficient to interrupt the nivolumab therapy if they are grade 4 or 5 as described below. Patients may be withdrawn from study even if DLT is due to decitabine alone.

Safety monitoring will include careful assessment and appropriate reporting of adverse events, as well as the construction and implementation of a data and safety-monitoring plan (Auditing, Monitoring and Inspecting). Medical monitoring will include a regular assessment of the number and type of serious adverse events. As this is a phase I study, all AEs will be reviewed by the Early Phase Clinical Trials committee at RPCI on a weekly basis.

Management and dose modifications associated with the above AEs are outlined in Section 10.3 and Appendix H.

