11.4 Evaluations Performed on Day 1 of each Cycle

The following evaluations will be performed prior to CDX-1401/poly ICLC dosing or infusion of decitabine on Day 1 of each cycle or prior to premedication, if administered (may be performed up to 3 days prior to day of infusion), unless otherwise indicated:

- Physical examination
- Vital signs (i.e., temperature, heart rate, respiratory rate, oxygen saturation, blood pressure, body weight)
- Hematology: CBC with manual differential (Once per week of each cycle during cycles 1-4, from cycles 5 onward on day 1 and as clinically indicated)
- Hematological Improvement (HI) in MDS or low blast count AML patients treated with the combination in order to provide descriptive characteristics.
 - This will be assessed using results of blood counts on day 1 of each cycle.
- Chemistry: CMP, LDH, uric acid, amylase and, lipase (Once per week each cycle during cycles 1-4, from cycles 5 onward on day 1 and as clinically indicated)
- ECOG performance status

PROTOCOL TITLE: I 49217 - Phase 1 CDX-1401/ Poly-ICLC +Decitabine +Nivolumab in Patients with MDS or Low Blast Count AML

- Correlative blood sampling prior to study drug dosing Once per week each cycle during Cycles 1-4; from Cycle 5 onward once every 2 weeks (see Section 11.11.1)
- Decitabine administration: Day 1-Day 5 of each cycle (per standard of care for patient safety)
- Nivolumab administration: Day 1 and Day 15 of each cycle (+/-7 days)
- Concomitant Medications
- Adverse events

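### The ±7-day dosing window is stated in conflicting ways, and on either reading about 7 rather than 14 DLT days can follow the second cycle 1 nivolumab and vaccine doses

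*Combined protocol and SAP*

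**What the plan says.** **The window.** Section 10.1.2 states "Nivolumab will be given every two weeks (± 7 days", with the tolerance attached to the interval. Section 11.4 attaches it to calendar days: "Nivolumab administration: Day 1 and Day 15 of each cycle (+/-7 days". Section 10.1 is wider: "Protocol therapy may be given at the discretion of the treating physician within a +/-7 day window". Its reasons include patient preference and scheduling, and doses may also be given "or outside this window after discussion with the PI".

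**The schedule.** Section 10.1 also says "For the purposes of this study, 1 cycle = 28 days" and keeps decitabine/nivolumab cycles four weeks apart unless a delay is clinically necessary. Section 10.1.3 gives decitabine "on days 1-5 followed by 23 days without decitabine", subject to the physician's standard practice, and mentions delay for patient safety as the reason to leave Days 1-5. No section states a minimum gap between nivolumab doses.

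**The DLT period.** Section 10.3: "The initial DLT period will be defined as 28 days after the first dose of decitabine". Section 8.1: "The DLT window will begin on day -14 of cycle 1 and end on day 1 of cycle 2". Section 7 gives its length as 6 weeks.

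**Its use.** Table 4 in Section 9.1 acts on the number of DLTs among 3 and then 6 patients. Section 9.2 replaces patients who do not reach Day 29 for reasons other than a DLT. It does not require that the Day 15 doses were given, or given on time. Section 19.5.1 treats anyone who received any study treatment as evaluable for toxicity.

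**The concern.** A tolerance of 7 days is half of the 14-day nivolumab interval, so it matters whether it is measured from the previous dose or from the nominal day. The sections give both versions and do not say which governs. They also differ on the grounds for moving a dose: convenience in either direction, or only a necessary delay.

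For the primary objective, the issue is what a DLT-free patient has been shown to tolerate. The DLT period in Section 10.3 is tied to the first decitabine dose and does not move with the Day 15 nivolumab and vaccine doses. If those doses come late, less of the period follows them, and the patient is still counted as having completed it. Table 4 turns on one versus two DLTs, so each patient's classification carries weight. The protocol expects late immune toxicity: Section 10.3 says that checkpoint-inhibitor effects may not show at once, and Sections 2.3.2 and 13.2 report onset from 4 days to 3.5 months in earlier studies.

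**Working it through.** This is calendar arithmetic; no sampling formula applies.

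**Inputs**
- Cycle length: 28 days (Section 10.1).
- Nivolumab in cycle 1: Days 1 and 15 (Section 11.4 and Table 5).
- Vaccine in cycle 1: Day 15, after the Day -14 dose (Section 10.1).
- Window: ±7 days (Sections 10.1, 10.1.2 and 11.4).
- DLT period: 28 days from first decitabine (Section 10.3), or Day -14 to cycle 2 Day 1 (Section 8.1).

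**The plan's own figure.** Taking Day -14 as 14 days before Day 1, the Section 8.1 window is 14 + 28 = 42 days = 6 weeks. This agrees with Section 7.

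**Gap between the two nivolumab doses in cycle 1**
- Interval reading (Section 10.1.2): 14 ± 7 = 7 to 21 days.
- Nominal-day reading (Section 11.4): each dose moves by up to 7 days, so the gap is 14 ± (7 + 7) = 0 to 28 days. The zero arises because Day 1 + 7 and Day 15 - 7 are both Day 8. Each window holds 15 days, so this is one pair out of 15 × 15 = 225.
- The same edge occurs at Day 22, between cycle 1 Day 15 + 7 and cycle 2 Day 1 - 7 (29 - 7 = 22).

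**DLT days left after the second doses.** With decitabine started on Day 1, the Section 10.3 period ends at Day 1 + 28 = Day 29. Days left = 29 - day of the second dose.

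| Case | Second nivolumab | Days left |
|---|---|---|
| On schedule | Day 15 | 29 - 15 = 14 |
| Nominal-day reading, latest | 15 + 7 = Day 22 | 29 - 22 = 7 |
| Interval reading, first dose on Day 1 | 1 + 21 = Day 22 | 29 - 22 = 7 |

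If the period is counted only to Day 28, the last two rows give 6. The vaccine is covered by the general window in Section 10.1 whichever nivolumab reading is used, so it too may fall on 15 + 7 = Day 22.

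**Sensitivity to the end of the period**
- Section 10.3 clock: if decitabine starts on Day 8, the period ends on Day 36, and 36 - 22 = 14 days remain. If it starts 7 days early, the period ends on Day 22 and 0 remain.
- Section 8.1 clock: with cycle 2 Day 1 on Day 22, 29 or 36, the days left are 0, 7 or 14.

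The zero cases need decitabine or cycle 2 to come early, which the text about delays argues against. The point therefore rests on 7 days, not 0.

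**The case against.** The strongest reply is that Section 10.1.2, the section on nivolumab dosing, never allows a zero gap if read as an interval, and that no clinician would give two doses on one day. This stands as far as it goes. A reader might infer that the protocol plans or accepts same-day nivolumab. It does not: this is one edge pair that arises only from the Section 11.4 wording. It shows that the sections need reconciling, and nothing more.

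A second reply is that combined exposure starts around Day 1, so a patient dosed late is still observed for about 28 days after first meeting all the agents. That is correct. Only follow-up after the second nivolumab and vaccine doses is shortened.

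A third is that late toxicity is watched in other ways: weekly adverse event review, 180 days of follow-up, and a hold on expansion until the first three patients reach cycle 4 day 29. The group window in Section 8.1 also runs until the last of the three patients reaches cycle 2. These are real safeguards. But the hold covers only the first three patients and lengthens nobody's DLT period, and the documents do not say that events found later enter the Table 4 count.

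Four stronger inferences are not supported:
- **Decitabine cycles may be compressed.** The decitabine text foresees delays only and defers to standard practice. The conflict with Section 10.1 needs reconciling, but no shortened rest period is established.
- **The vaccine lead-in may vanish.** That depends on a day-numbering convention that the documents do not state.
- **Blood samples lose their link to dosing.** Sections 11.4 and 11.7 call for correlative sampling before study drug, which answers much of this.
- **The window causes harm.** Nothing shows this. Section 2.3.2 reports no pattern of nivolumab adverse events by dose level.

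**Conclusion.** The point holds in two parts. First, the window is stated inconsistently: 7 to 21 days between nivolumab doses on one reading and 0 to 28 on the other, with conflicting grounds for moving any dose. Second, on either reading the second nivolumab and vaccine doses may fall on Day 22, leaving about 7 of the 28 DLT days after them, half of the scheduled 14. The patient would still count as DLT-free in Table 4.

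The second part assumes that decitabine starts on Day 1 and, on the interval reading, that the first nivolumab dose is also given on Day 1. If decitabine starts late, the Section 10.3 clock moves with it and the shortfall shrinks or disappears. How often late dosing will occur cannot be judged from the documents. The weakness is therefore one that the wording allows, not a demonstrated bias. It should be corrected because safety is the primary objective, the decision rule uses very few patients, and the correction is small.

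**What to change.** **Reconcile the window.** The sponsor should bring Sections 10.1, 10.1.2, 10.1.3 and 11.4 into agreement so that one reading governs: what the tolerance is measured from, which agents it covers, and on what grounds a dose may move. All dosing values are for the sponsor's clinicians.

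**Define DLT evaluability by actual dosing dates.** In Sections 9.2 and 10.3, state that a patient counts as DLT-free only after receiving the cycle 1 Day 15 nivolumab and vaccine doses and completing a sponsor-set observation time after them. Extend the DLT period when those doses are late. A patient with a DLT counts as such whether or not the Day 15 doses were given. Also state how a patient is counted whose Day 15 doses were withheld for a toxicity that is not a DLT, since simply replacing such patients could make the regimen look safer than it is. Align Sections 7 and 8.1 with the result.

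**Cost.** A few sentences. The DLT decision for a late-dosed patient may wait up to about a week longer. For illustration only, if the observation time equalled the scheduled 14 days, doses on Day 22 would move the end to 22 + 14 = Day 36, which is 36 - 29 = 7 days later. Patients dosed on schedule would see no change in that case.
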